#### 5. STUDY SUBJECTS

#### 5.1 Disposition of Subjects

The following will be summarized in the disposition table:

- The number of subjects screened
- The number and percent of subjects who failed screening and screen failure reasons
- The number of subjects included in the SAS
- The number of subjects included in the FAS
- The number and percent of subjects in Cohort 1 and in Cohort 2 who completed as per protocol, for both the FAS and the SAS
- The number and percent of subjects in Cohort 1 and in Cohort 2 who withdrew prior to completing the study, and associated primary reason for withdrawal, for both the FAS and the SAS

These summaries will be tabulated within cohort and treatment group as well as overall.

#### 5.2 **Protocol Deviations**

All protocol deviations will be listed, sorted by treatment group, then investigative site and subject number, and date of protocol deviation.

#### 5.3 Demographic and Baseline Characteristics

Descriptive statistics will be used to summarize the demographic and baseline characteristics (age, gender, race, ethnicity, baseline vital signs, and pertinent medical history) for the SAS, by cohort and treatment group.

#### 5.4 Medical History

All medical conditions and surgical procedures will be classified by system organ class (SOC) and preferred term (PT) using the Medical Dictionary for Regulatory Activities (MedDRA). The number and percent of subjects with each medical condition and surgical procedure will be presented for each SOC and PT for the SAS, by cohort and treatment group.

#### 5.5 **Prior and Concomitant Medications**

Concomitant medications will be categorized into either non-immunosuppressant medications, immunosuppressant medications, or medications given as part of surgical procedures. Summaries of each category will be presented separately. Diabetic medications will not be included.

All prior and concomitant medication data will be listed, sorted by treatment group, then

investigative site and subject number, start and stop date. Information listed will include medication, indication, dose, frequency and route of administration.

For VC02-102, all doses of insulin will be listed, sorted by treatment group, then investigative site and subject number, and date of administration. Information listed will include type of insulin and total units taken for the entire day.

All medications will be coded using World Health Organization (WHO) drug classifications. The number and percent of safety subjects will be tabulated by Anatomical, Therapeutic, and Chemical (ATC) class and by preferred name.

# 6. EFFICACY ANALYSIS

All efficacy summaries/analyses will be performed on the VC02-101 FAS. Subjects will be summarized by cohort and treatment group.

## 6.1 **Primary Efficacy Endpoint and Analysis**

## Primary Endpoint / Cohort 2:

Change from baseline to Week 26 in C-peptide  $AUC_{0-4h}$  following an MMTT will be analyzed using analysis of covariance (ANCOVA), with treatment group as a factor and baseline C-peptide  $AUC_{0-4h}$  as a covariate. The FAS (Cohort 2 subjects who meet the FAS criteria) will be used to analyze the primary efficacy endpoint. The output from the ANCOVA will include the least squares mean (LSM) and standard error (SE) for each treatment group.

A listing of the 4-hr MMTT/C-Peptide and Glucose results will be provided.

## 6.2 Secondary Efficacy Endpoints and Analyses

Each of the secondary efficacy endpoints will be analyzed using an  $\alpha = 0.05$  level of significance. Given the large number of secondary efficacy endpoints, the p-values for these endpoints will be considered descriptive.

For all secondary efficacy analyses, the FAS (Cohort 2 subjects who meet the FAS criteria) will be used. Change from baseline in C-peptide AUC0-4h following an MMTT at Weeks 52, 78, and 104 and change from baseline in C-peptide AUC0-2h following an MMTT at Weeks 8, 12, 16, 20, 39, 52, 65, 78, 91, and 104 will be analyzed in a similar manner to the ANCOVA performed for change from baseline in C-peptide AUC0-4h at Week 26, with the relevant baseline as the covariate. For subjects who continue to have a C-peptide  $\leq 0.1$  ng/mL as determined by the simplified oral glucose challenge test, the AUC of the respective 2-hour MMTT will be set to 0. A listing of the 2-hr MMTT/C-Peptide and Glucose results will be provided, as well as a listing of the simplified oral glucose challenge.

Time to onset of biological response of C-peptide following MMTT will be assessed using Kaplan-Meier (KM) product-limit method, with the p-value from the logrank test also provided.

The number and percent of subjects achieving a positive stimulated C-peptide (defined as > 0.2 ng/mL) after implant will be analyzed using Fisher's exact test. The number and percent of subjects in each treatment group and the p-value from the Fisher's test will be provided (at each time point, where appropriate).

Change from baseline in frequency of hypoglycemic events (24-hour; daytime [start between 6 a.m. -12 a.m.]; nocturnal [start between 12 a.m. -6 a.m.]) at Weeks 16, 26, 52, 78 will be analyzed using ANCOVA, with treatment group as a factor and the relevant baseline as a covariate. This analysis will be performed using HEs from both the patient-reported diary and from CGM. A listing of hypoglycemic events will be provided for both patient-reported data and from CGM data.

The number and percent of subjects free of severe hypoglycemic events between study visits (Weeks 16-20, Weeks 20-26, ..., Weeks 91-104, and Weeks 16-104) will each be analyzed using Fisher's exact test. The number and percent of subjects in each treatment group and the p-value from the Fisher's test will be provided (at each time point, where appropriate). These analyses will be performed using both HEs from patient-reported diary and HEs from CGM.

Change from baseline to Weeks 16, 26, 52, 78 and 104 in Clarke score will be analyzed using ANCOVA, with treatment group as a factor and the relevant baseline as a covariate. A listing of the Clarke total score will be provided.

Change from baseline to Weeks 16, 26, 39, 52, 78 and 104 in average daily insulin requirement in the seven days preceding the clinic visit will be analyzed using ANCOVA, with treatment group as a factor and the relevant baseline as a covariate. A listing of insulin dosing will be provided.

The number and percent of subjects who achieve a 50% reduction in average weekly exogenous insulin dose from baseline to Weeks 16, 20, 26, 39, 52, 78, and 104 will each be analyzed using Fisher's exact test. The number and percent of subjects in each treatment group and the p-value from the Fisher's test will be provided (at each time point, where appropriate).

The number and percent of subjects who achieve exogenous insulin independence (both definitions will each be analyzed using Fisher's exact test. The number and percent of subjects in each treatment group and the p-value from the Fisher's test will be provided (at each time point, where appropriate).

Percent of time spent with blood glucose values at various cut points at each scheduled visit will be summarized descriptively. The coefficient of variation (CV) of blood glucose values will be included in the summary. The percentages and change from baseline percentages will be summarized for each cut point (<54 mg/dL,  $\geq$ 54 to <70 mg/dL,  $\geq$ 70 mg/dL to  $\leq$ 180 mg/dL,  $\geq$ 180 mg/dL, and >250 mg/dL) and for each treatment group. The number of subjects with Prolonged HEs (duration > 120 minutes for cut points  $\leq$ 54 mg/dL and  $\leq$ 70 mg/dL) will also be summarized.

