## 7.10.2. Continuous Glucose Monitoring (CGM)

All subjects will be provided with a CGM system. Previous experience with CGM is not a requirement of study entry, but all subjects are required to use the Sponsor-provided CGM during study participation. Based on the labeled indication of the CGM in use, diabetes treatment decisions may be based on CGM data collected. Subjects relying on CGM data for treatment decisions will be required to be compliant with CGM usage and wear the CGM for the entire two-year study and also periodically sync the data, so that near-real time access may be available to the Investigator and Sponsor. A study reference manual will further outline the logistics with respect to CGM use and data collection.

All CGM supplies and instruction manuals will be provided by the Sponsor. Site personnel will instruct the subject on proper use and care at Visit 2 (Week -4) and as needed throughout the study. This training includes assisting the subject with the insertion of the first sensor needle prior to leaving the clinic at Visit 2. The CGM system is configured to alert the subject in the event blood glucose values approach hypoglycemic levels.

The CGM data collected for this trial will be used to evaluate secondary and exploratory endpoints. Data from the two weeks prior to appropriate clinic visits will be used in order to calculate the CGM endpoints (e.g., percent of time a subject's blood sugar is <54 mg/dL,  $\geq 54 \text{ to } <70 \text{ mg/dL}$ ,  $\geq 70 \text{ mg/dL}$ , and >180 mg/dL). Other endpoints using CGM data may be evaluated and, if so, will be described in the Statistical Analysis Plan (SAP).

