#### Secondary Efficacy Endpoints:

#### *VC02-101*:

- Change from baseline to Weeks 8, 12, 16, 20, 26, 39, 52, 65, 78, 91, and 104 in C-peptide area under the curve from 0 to 2 hours (AUC0-2h) or AUC0-4h following an MMTT;
- Time to onset of biological response of C-peptide following MMTT;
- Percent of subjects achieving a positive stimulated C-peptide (defined as >0.2 ng/mL) after implant;
- Change from baseline to Weeks 16, 26, 39, 52, 78, 104 in weekly frequency of hypoglycemic events;
- Percent of subjects free of severe hypoglycemic events between study visits starting with Week 16 (i.e., Weeks 16-20, Weeks 20-26, Week 26-39, Weeks 39-52, Weeks 52-65, Weeks 65-78, Weeks 78-91, Weeks 91-104);
- Percentage of subjects free of severe hypoglycemic events between Week 16 and Week 104 (or early termination).
- Change from baseline to Weeks 16, 26, 39, 52, 78 and 104 in Clarke score;

- Change from baseline to Weeks 16, 26, 39, 52, 78, and 104 in average daily insulin dose;
- Percent of subjects who achieve a 50% reduction in average weekly exogenous insulin requirements from baseline to Weeks 16, 20, 26, 39, 52, 78, and 104;
- Percent of subjects who achieve exogenous insulin independence;
- Percent of time spent with blood glucose values at various cut points (e.g., <54 mg/dL, ≥54 to <70 mg/dL, ≥70 mg/dL to ≤180 mg/dL, >180 mg/dL, and >250 mg/dL) as measured by each subject's continuous glucose monitoring (CGM) device.
- Change from baseline to Weeks 16, 26, 39, 52,78, and 104 in time-in-euglycemic range (≥70 mg/dL to ≤180 mg/dL), time-in-hypoglycemic ranges (<54 mg/dL and ≥54 to <70 mg/dL), and time-in-hyperglycemic ranges (>180 mg/dL and > 250 mg/dL) as measured by each subject's CGM.

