## 4.6.4 Frequency of hypoglycemic events using CGM data

CGM will also be utilized, based on the below specified rules, to evaluate the number of hypoglycemic episodes (number of times blood glucose falls below 70 mg/dL) and the number of severe hypoglycemic events (number of times blood glucose falls below 54 mg/dL) for each subject:

- A set of CGM readings < 70 mg/dL or <54 mg/dL, with a minimum overall duration of 15 minutes
- Up to two consecutive readings >= 70 mg/dL (or >= 54 mg/dL for separate summary) are allowed within the same episode
- If a subsequent episode starts within 60 minutes of the start of the previous episode, then they are combined and counted only as one episode

The total number (over the entire 24-hour time period) of episodes will be calculated as well as the number of nocturnal (starts during the 12 a.m. - 6 a.m. period) episodes and the number of daytime (starts during the 6 a.m. to 12 a.m.) episodes.

Baseline CGM-reported HE data will be calculated using up to 28 days of data. Baseline CGM-reported HEs will be recorded starting at Day -3 (i.e., the day prior to immunosuppression induction) and working backwards for up to 28 days (through Day -30). For instances in which the available pre-implant dataset provides <28 days of data, the dataset will be supplemented with post-implant data, using data from Day 4 forward until 28 days of data is available. Data from days on which an MMTT or SOGCT was performed, will not be included in the calculation. These

data will be used to calculate the baseline number of weekly total episodes, weekly nocturnal episodes, and weekly daytime episodes. In addition, the CGM data from the 14 days prior to each scheduled clinic visit will be used to calculate the number of weekly total episodes, the number of weekly nocturnal episodes, and the number of weekly daytime episodes for each of these visits. Data should not be used if an MMTT or SOGCT was performed on that day.

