#### 4.6.7 Percent of time spent with blood glucose values at various cut points

Subjects in Cohort 2 of Study VC-02-101 are required to wear their CGM, at minimum, during the 30-day period prior to their scheduled clinic visits, although wearing of the CGM for the entire two-year study is encouraged. The cut points of <54 mg/dL,  $\ge54 \text{ to } <70 \text{ mg/dL}$ ,  $\ge70 \text{ mg/dL}$  to  $\le180 \text{ mg/dL}$ , >180 mg/dL, and >250 mg/dL will be assessed. Also, severe HEs characterized by an altered mental and/or physical status requiring assistance will be summarized.

The summarization will be performed three ways: over the entire 24-hour time period, over the nocturnal (CGM value below/above the cut point occurs between 12 a.m. - 6 a.m.) time period, and over the daytime (CGM value below/above the cut point occurs between 12 a.m. - 6 a.m.) time period.

Baseline CGM data will be utilized to calculate percentages spent with blood glucose values at the various cut points for up to 28 days, starting at Day -3 (i.e., the day prior to immunosuppression induction) and working backwards for up to 28 days (through Day -30). For instances in which the available pre-implant dataset provides <28 days of data, the dataset will be supplemented with post-implant data, using data from Day 4 forward until 28 days of data is available. Data should not be used if an MMTT or SOGCT was performed on that day. In addition, the CGM data from the 14 days prior to each scheduled clinic visit will be used to calculate percentages spent with blood glucose values at the various cut points for these visits.

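### CGM-based event-free percentages cover whole between-visit intervals, but the SAP requires sensor wear only in the 30 days before each visit and sets no wear or evaluability rule

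*SAP*

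**What the plan says.** The secondary endpoint list in SAP 2.2.2 defines eight intervals for the severe-event-free percentage: "Weeks 16-20, Weeks 20-26, Week 26-39, Weeks 39-52, Weeks 52-65, Weeks 65-78, Weeks 78-91, Weeks 91-104". It adds a separate percentage for Weeks 16-104 or early termination. SAP 6.2 analyses each by Fisher's exact test across treatment groups, in the Cohort 2 Full Analysis Set, from two sources: "These analyses will be performed using both HEs from patient-reported diary and HEs from CGM".

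For the CGM source, SAP 4.6.4 counts an episode below 54 mg/dL lasting at least 15 minutes as a severe event. Its only post-baseline period is for weekly frequency: "the CGM data from the 14 days prior to each scheduled clinic visit will be used to calculate the number of weekly total episodes". It has no rule for the between-visit intervals.

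On wear, SAP 4.6.7 says that Cohort 2 subjects "are required to wear their CGM, at minimum, during the 30-day period prior to their scheduled clinic visits". Continuous wear is a recommendation there, not a duty. Protocol 7.10.2 requires all subjects to use the sponsor's CGM while in the study, without stating a minimum wear time. It then sets a stricter duty for a subset: "Subjects relying on CGM data for treatment decisions will be required to be compliant with CGM usage", with wear over the full two years.

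SAP 4.4 rules out imputation beyond the MMTT and adverse-event-date rules listed there. By comparison, SAP 4.6.6.1 divides insulin doses by the number of days with data and requires at least four such days.

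**The concern.** The interval analysed is longer than the interval in which observation is required. The endpoint is yes or no for each subject, and the plan has no third category for subjects not observed long enough. Time without a sensor can hide an episode but cannot create one, so any gap moves the CGM-based percentage upward.

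Two readings of the results are at stake. The first is the percentage itself, which may enter the descriptive Week 26 report or the later efficacy review. The second is the comparison between treatment groups (numbers of VC-02-300 units): if groups differ in wear, they differ in the chance of detecting an episode even when true rates are equal. The subset rule in Protocol 7.10.2 makes some difference in wear between subjects likely by design.

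**Working it through.** Neither document states a CGM coverage figure for this endpoint, so there is no plan figure to reproduce.

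**Inputs.** Interval bounds are from SAP 2.2.2 and 6.2. Minimum wear of 30 days before each visit is from SAP 4.6.7. Nominal visit weeks are used.

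**Coverage at minimum wear.** Required observed days = min(30, interval days).

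| Interval | Days | Required observed | Unobserved | Share unobserved |
|---|---|---|---|---|
| Weeks 16-20 | 28 | 28 | 0 | 0% |
| Weeks 20-26 | 42 | 30 | 12 | 28.6% |
| Each of six 13-week intervals, Weeks 26-104 | 91 | 30 | 61 | 67.0% |
| Weeks 16-104 | 28 + 42 + 6 × 91 = 616 | 28 + 30 + 6 × 30 = 238 | 378 | 61.4% |

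Visit windows can lengthen an interval. With +/-14 days at both ends, 91 days becomes 119, and (119 − 30)/119 = 74.8% is unobserved.

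**Effect on the 13-week percentage.** Assume a constant episode rate r per week, with episodes independent in time. Then:

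- true event-free share = exp(−r × 91/7) = exp(−13r)
- counted share at minimum wear = exp(−r × 30/7)

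The documents give no CGM episode rate, so a range is shown.

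| r per week (assumed) | True | Counted |
|---|---|---|
| 0.01 | 88% | 96% |
| 0.05 | 52% | 81% |
| 0.1 | 27% | 65% |
| 0.5 | 0.2% | 12% |
| 1 | about 0% | 1.4% |

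The gap is largest where r = ln(91/30)/(13 − 30/7) = 1.110/8.714 = 0.127 per week (19% against 58%). It shrinks at lower and higher rates.

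**Effect on a group comparison.** Take two groups of 20 (an assumed size), both with a true 13-week event-free share of 50%. One wears the sensor continuously and the other only for the 30 required days. The expected counts are 10 of 20 and 20 × 0.5^(30/91) = 15.9, or 16 of 20. Fisher's exact p is 0.096 with no true difference.

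**Weekly counts.** The 14-day window of SAP 4.6.4 lies inside the 30 days of required wear, so the gap above does not arise there. What is missing is narrower. No formula says what the episode count is divided by, although MMTT and SOGCT days are excluded, and no minimum amount of sensor data is set. Baseline is topped up until 28 days of data exist; post-baseline has no counterpart.

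**The case against.** The strongest reply is that the protocol governs conduct. Protocol 7.10.2 requires every subject to use the CGM during participation, inclusion criterion 7 asks for willingness to use it as instructed, and the schedule of assessments reviews CGM data at each visit from Visit 2 to Visit 17. The 30-day minimum appears only in the SAP, in the section on percent of time in range. This stands in part: the two documents set different requirements, and two thirds is a ceiling at minimum wear, not an expected value. It does not close the gap, because the protocol states no wear minimum for subjects who do not treat from CGM, and even full required wear leaves actual gaps without a rule.

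A second reply is that no passage says unworn time counts as event-free. A reader might infer that the SAP prescribes this. It does not: its rule that blanks are zero is confined to the diary log of hypoglycemic events (SAP 4.6.3). The counting follows by implication from a yes/no endpoint on the full set with no evaluability rule.

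A reader might also infer that the error favours the product and grows over the two years. The documents do not support that. The event-free endpoint has no baseline comparison and the trial has no control arm. Minimum-wear coverage is a constant 33% in every interval from Week 26, and falling wear is not documented.

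Finally, p-values for secondary endpoints are declared descriptive, no hypotheses are tested, and the diary version is reported alongside. That limits the weight of the point. The diary version uses a different event (assistance needed), so it cannot correct the CGM percentage.

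**Conclusion.** The point holds in a limited form. The CGM-based event-free percentage is defined over intervals that the SAP does not require to be observed, and nothing says how unobserved time is handled. At minimum wear, up to 67% of each 13-week interval and 61% of Weeks 16-104 is unobserved; Weeks 16-20 has no gap and Weeks 20-26 has 29%. Subjects who wear the sensor continuously are unaffected.

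The direction is certain whenever wear is incomplete and such subjects are tabulated as free: the percentage is too high. The size is not known. It rests on actual wear and on an episode rate that must be assumed; under a constant rate the 13-week overstatement runs from about 8 points at 0.01 per week to 38 points at 0.1, and falls again at higher rates. Bias between treatment groups arises only if wear differs between them. The point affects one of two versions of a descriptive secondary endpoint, not the primary analysis.

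**What to change.** 1. Reconcile SAP 4.6.7 with Protocol 7.10.2, so that one wear requirement applies to all Cohort 2 subjects or the difference between subsets is stated.
2. In SAP 6.2, for the CGM version, choose one of two routes. Either restrict the event-free percentage to the 30-day pre-visit window (cut at the preceding visit where the interval is shorter), among subjects meeting a prespecified minimum of sensor data. Or replace the between-visit and Weeks 16-104 versions with episode rates per sensor-day, from a count model with log sensor-days as offset. Report sensor-days by treatment group in both cases.
3. In SAP 4.6.4, define weekly CGM episodes as 7 × episodes / days with sensor data, with the same prespecified minimum at baseline and post-baseline, as SAP 4.6.6.1 already does for insulin.

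The minimum is for the sponsor to set in advance. A threshold of 70% of readings is one option and is not drawn from the documents.

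The cost is SAP wording and programming, plus a protocol clarification if the wear requirement is settled there; no new data are needed. Some poorly observed subject-visits become non-evaluable. The window route discards episodes seen outside the 30 days in continuous wearers and answers a narrower question. The rate route keeps them but assumes that the rate while worn represents the rate while not worn.

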# 6.3 Pharmacokinetic and Pharmacodynamic Analyses

There will be no pharmacokinetic or pharmacodynamics testing done in this study.

# 7. SAFETY ANALYSIS

Unless otherwise specified, the VC02-101 and VC02-102 SAS (both Cohort 1 and Cohort 2 subjects who meet the SAS criteria) will be used for the primary safety summarizations. Other safety data, such as vital signs and clinical laboratory data will be summarized by study visit and treatment group. Where appropriate, change from baseline in safety data will also be summarized in a similar manner.

For the secondary safety endpoint of confirmed immune sensitization defined by presence of donor anti-HLA antibodies absent prior to implant with either confirmatory histological observations

from at least one explanted unit and/or the presence of clinical symptoms will have all relevant data described in a clinical narrative. In addition, data of interest from the assays may be summarized by cohort and treatment group as well as overall.

